14 STATISTICAL SECTION

14.1 SAMPLE SIZE

Up to 18 patients may be enrolled in the Dose Escalation part of this study, in cohorts of 3 or 6 patients at each specified dose. Patients must take at least 80% of their prescribed doses to be considered eligible for MTD evaluation. Sixteen patients will be enrolled in the Dose Expansion part of this study.

These sample sizes are not based on statistical considerations but are deemed sufficient to determine the MTD for and to describe the pharmacokinetic characteristics of this agent.

An expansion cohort of N=16 will allow a total sample size of up to 34 patients. If the expected response rate is 18% (6/34) for a hypothetical comparator and the expected response rate of NOX66 will be 24% (8/34) in the current NOX66-004 trial, this sample size ensures an 85% probability that the observed response rate of NOX66- will be greater than 18%.

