	
 • Complete blood count • Electrolytes (Ca⁺⁺, Mg⁺⁺), PO₄, BUN, creatinine 
The following criteria will be used to evaluate the efficacy of NOX66 alone and in combination with doxorubicin:
 
 • RECIST v1.1: Disease Control Rate (DCR) defined as [(stable disease (SD) + partial response (PR) + complete response (CR)/All)], overall response rate (ORR) • Overall survival (OS), Progression Free Survival (PFS) • European Organization for Research and Treatment of Cancer: Core Quality of Life Questionnaire v3.0 (EORTC QLQ-C30) • Fatigue Severity Scale (European Organisation for Research and Treatment of Cancer: Cancer Related Fatigue Module - EORTC QLQ-FA12) • Brief Pain Inventory (short form) • Suppository Acceptance Questionnaire 
The following criteria will be used to evaluate the PK of idronoxil and metabolites in blood plasma after single and repeated doses of NOX66:
 
 • Maximum concentration (C_{max}) • Time to reach maximum concentration (T_{max}) • Trough concentrations after repeated administration • Area under the concentration-time curve up to last measurable time point and infinity (AUC_{last} and AUC_{inf}) • Area under the concentration-time curve over a dosing interval after repeated administration (AUC_T) • Terminal elimination half-life (if possible) 
Pharmacokinetic parameters of idronoxil and metabolites obtained on Day 7 will be compared to Day 1 values. Sparse PK sampling for determination of idronoxil and metabolites, doxorubicin and doxorubicinol concentrations will be obtained during the treatment cycles to assess variability of exposure of idronoxil and doxorubicin in an exploratory manner.
 
The following biomarkers will be evaluated to assess the relationship between response to NOX66 and doxorubicin:
 
 • Genetic mutations • Change in lipid profile from baseline • Cytokine/chemokine and ENOX2 dynamics
Number of Patients (Planned)	Up to approximately 34 patients with metastatic soft tissue sarcoma will be studied if the MTD is determined with the maximum dose planned for this study. If a minimum number of patients is studied per dose escalation, the expected number of patients is approximately 28.

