	
replaced in the Monotherapy period, in Cycle 1 or 2, the number of patients will be higher than 34.
 
Analysis sets:
 
There will be two analysis sets
 
• Safety Set: All patients treated with at least one dose of idronoxil will be included in the Safety Set (SS). All analyses of safety, toxicity, and PK will be performed for this set.• Full Analysis Set (FAS): All patients who completed at least one cycle of combination therapy (at any NOX66 dose). 
Analyses of efficacy, tolerability, and biomarkers will be performed for the FAS. Separate summaries may be provided for patients participating in the Dose Escalation and Dose Expansion parts.
 
Safety (Primary analysis):
 
The safety profile will be based on Serious Adverse Events (SAEs), Treatment Emergent Adverse Events (TEAEs), standard clinical laboratory parameters (clinical chemistry, hematology, urinalysis), vital signs measurements, ECG parameters, and physical examination findings.
 
Adverse events (AE) will be coded using the Medical Dictionary for Regulatory Activities and summarized by dose when NOX66 is given alone or in combination with doxorubicin. The number and percentage of patients reporting TEAEs will be calculated overall, by system organ class, and by preferred term for each dose level. Adverse events will also be graded for severity according to the National Cancer Institute Common Terminology Criteria for Adverse Events, Version 5.0.
 
Serious Adverse Events (SAEs) will be summarized separately.
 
Cardiac AEs (including clinically significant abnormalities in ECG rhythm and waveform morphology reported as TEAEs) and changes in echocardiographic parameters will be summarized.
 
Descriptive statistics will be provided for demographics, baseline characteristics, and exposure to treatment by cohort.
 
Univariate summary statistics will be provided by dose group at each visit for quantitative laboratory parameters and vital signs and for the change from baseline in these parameters. For laboratory values and vital signs with defined CTC grades, shift tables will be provided for CTC grades from baseline to end of study and from baseline to worst value on study.
 
Univariate summary statistics will be presented for ECG parameters for the value at each measurement time point and the change from baseline to each measurement time point. A similar analysis will be provided for the worst value of each ECG parameter on study.
 
Findings from physical examinations and ECOG performance status will be summarized by dose of NOX66 given alone or in combination with doxorubicin.
 
Pharmacokinetics (Secondary analysis):
 
Individual blood concentration-time data and blood PK parameters will be summarized using descriptive statistics by dose and sampling time for idronoxil and metabolites. Separate summaries will be provided for PK

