--	--

	
samples collected for single-dose administration, repeated administration, and administration in combination with doxorubicin.
 
Blood PK parameters will be determined by noncompartmental analysis for idronoxil and metabolites and will be summarized by dose and treatment day. Concentrations of idronoxil obtained in the presence of doxorubicin will be compared to monotherapy.
 
Concentrations of doxorubicin and doxorubicinol will be determined after the administration of the infusion in the presence of NOX66 and will be compared to historical controls.
 
The relationship between PK parameters and AEs and other safety findings may be assessed by graphical methods and special summary tables.

	
Efficacy (Secondary analysis):
 
The DCR, ORR, and the incidences of CR, PR, SD, and Progressive Disease (PD) as assessed by RECIST v1.1 criteria will be summarized for the MTD of the combination by counts and percentages and exact 95% confidence intervals at the end of Cycles 2, 4, and 6, at the 6-month, 9-month, and 12-month follow-up visits and at End of Study.
 
Survival functions will be computed for OS and PFS by the Kaplan-Meier method. Estimates of median OS and median PFS will be presented.

	
Quality of Life (Secondary Analysis):
 
Quality of Life analyses will be performed for the FAS. Scale measures from the EORTC QLQ will be presented by dose for each visit, along with change from baseline to each visit. Brief pain inventory items and fatigue parameters will be summarized by dose at each visit as well as the change from baseline to each visit.

	
Exploratory Analysis:
 
An exploratory analysis will be performed to assess various factors which may contribute to response to the combination of NOX66 and doxorubicin. These factors include, NOX66 dose or exposure, cytokine, chemokine and ENOX2 response, lipidomic profiling (capturing over 300 lipid species as determined by liquid chromatography-tandem mass spectrometry), histopathology, and specific genetic mutations. The acceptability of the suppository dosage form by patients will also be determined.

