14.3 STATISTICAL METHODOLOGY

14.3.1 GENERAL STATISTICS METHODS

All data will be summarized by idronoxil dose group. For safety analyses, a summary group consisting of all dose groups combined may also be presented.

For all measurements, the baseline value will be the last measurement taken before the first dose of study drug, whether idronoxil or of idronoxil + doxorubicin depending on the cohort.

Standard summary statistics will be presented for all measurements. For continuous variables, the standard summary statistics will be the number of observations (n), mean, standard deviation, median, minimum and maximum. For categorical variables, the standard summary statistics will be the number and percentage of observations in each category. Categories that are specified on the eCRF which contain no observations will be presented in the data summaries with a value of 0.

An AE with a completely missing start date will be assumed to start one minute after the date-time of the first idronoxil dose. If the severity of a reported AE is missing, it will be assumed that the event is severe; similarly, if the relationship of a reported AE to study treatment is missing, it will be assumed that the event is definitely related to treatment. No other missing data will be imputed. Incomplete start dates for Adverse Events and Concomitant Medications and incomplete end dates for AEs will have missing parts imputed by a conservative procedure which will be specified in the Statistical Analysis Plan (SAP).

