14.3.10 EFFICACY ANALYSES

Treatment response will be assessed by RECIST v1.1 criteria for patients in the FAS at the end of Cycles 2, 4, and 6, at the 6-month, 9-month, and 12-month follow-up visits, and at the End of Study or Early Termination. Along with CR, PR and SD, the ORR will be defined as the relative frequency of patients with either CR or PR, and the DCR will be defined as the relative frequency of patients with CR, PR, or SD.

The ORR, the DCR, and the frequencies of CR, PR, SD, and PD will be summarized at the end of Cycles 2, 4 and 6 and at the 6-month, 9-month, 12-month and up to 18-month follow-up visits. A summary will also be provided of best response on study.

At the assessment at the end of Cycle 6, a one-sided exact binomial test will be used to test the null hypothesis that the ORR is no greater than 0.20 (20%) against the alternative hypothesis that the ORR is greater than 0.20 at an approximate level $p = 0.025$. A similar test against the performance level of 0.20 will be performed for the rate of best objective response on study.

Overall survival will be defined as the time in months from initial treatment until death or censoring. Patients not known to have died at the time of analysis will be censored at the time of last contact with study personnel., including patients who are lost to follow-up. The overall survival curve will be estimated for the FAS by the Kaplan-Meier method.

Progression-free survival will be defined as the time in months from initial treatment until death, disease progression, or censoring. Patients who are lost to follow-up will be censored at the time of their last contact with study personnel. Patients who leave the study to begin an alternative therapy will be censored on their day of study discontinuation. The PFS curve will be estimated for the FAS by the Kaplan-Meier method.

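### Section 14.1 gives an 85% chance that the observed response rate exceeds 18% with 34 patients; for that event as worded the probability is 72–74%.

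*Combined protocol and SAP*

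**What the plan says.** Section 14.1 first says that the sample sizes were not chosen on statistical grounds. It then adds a quantitative statement. The total is a ceiling: "An expansion cohort of N=16 will allow a total sample size of up to 34 patients". The benchmark is set by supposing that "the expected response rate is 18% (6/34) for a hypothetical comparator", and the expected rate with NOX66 is put at 24% (8/34). From these inputs the section concludes that "this sample size ensures an 85% probability that the observed response rate of NOX66- will be greater than 18" per cent. No formula or derivation is given.

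The total of 34 is not fixed. The synopsis (Number of Patients) says that with minimum cohort sizes "the expected number of patients is approximately 28", and its sample-size paragraph says that if patients are replaced "the number of patients will be higher than 34".

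The only efficacy test is in section 14.3.10. It uses a different benchmark: "the null hypothesis that the ORR is no greater than 0.20 (20%) against the alternative hypothesis that the ORR is greater than 0.20", at a one-sided level of about 0.025.

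**The concern.** With 34 patients the observed rate can only move in steps of 1/34, about 2.9 percentage points. One responder either side of the threshold therefore changes the probability a good deal, and it matters whether the event is stated as exceeding the benchmark or as reaching it. The section writes the first, but its figure looks like the second.

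This is the only probability offered in support of the sample size, and an ethics committee or investigator will read it as an assurance about the chance of beating the comparator. If it belongs to the weaker event, the chance of exceeding the comparator is overstated. The reader also cannot see how often a regimen with no advantage would pass.

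**Working it through.** **Inputs (all from section 14.1).** n = 34; comparator 18%, also written 6/34 = 17.65%; expected rate 24%, also written 8/34 = 23.53%; stated probability 85%. Because the section gives each rate in two forms, both are carried through.

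**Formula.** With X responders among 34 and true rate p, P(X ≥ r) is the sum over x = r to 34 of C(34, x) p^x (1 − p)^(34 − x).

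**Reproducing the printed figure.** With r = 6 (observed rate at least 6/34):

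- p = 8/34: P(X ≥ 6) = 0.8445
- p = 0.24: P(X ≥ 6) = 0.8589

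These bracket 85%, so this is the event that the figure fits.

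**The event as worded.** 6/34 = 17.65% is below 18%, and 7/34 = 20.6% is above it. Reading 18% as exactly 6/34 changes nothing, since six responders would equal the threshold and not exceed it. Both readings need r = 7:

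- p = 8/34: P(X ≥ 7) = 0.7197; shortfall 0.85 − 0.7197 = 0.130
- p = 0.24: P(X ≥ 7) = 0.7407; shortfall 0.85 − 0.7407 = 0.109

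The gap between the two events is the probability of exactly six responders: 0.8445 − 0.7197 = 0.125, or 0.8589 − 0.7407 = 0.118. For P(X ≥ 7) to reach 85%, the true rate would have to be about 27%.

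**If the regimen is no better than the comparator.**

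| Event | p = 6/34 | p = 0.18 | p = 8/34 | p = 0.24 |
|---|---|---|---|---|
| At least 7 (above 18%) | 0.393 | 0.415 | 0.720 | 0.741 |
| At least 6 (at least 6/34) | 0.570 | 0.591 | 0.845 | 0.859 |

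**Other routes to 85% for the worded event.**

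- Normal approximation without continuity correction: 77.6–80.7% with the standard error at the true rate, 79.9–83.4% with the standard error at the benchmark rate.
- Normal approximation with continuity correction for strict exceedance: 71.2–74.7%.
- Comparison with a second group of 34 patients at the comparator rate: 66–79%.

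None reaches 85%. The closest, 83.4%, pairs a 24% true rate with a 6/34 threshold and uses the benchmark variance under the alternative.

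**Other totals.** The number of responders needed to exceed 18% is recomputed for each n.

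| n | Needed | p = 8/34 | p = 0.24 |
|---|---|---|---|
| 28 | 6 | 0.674 | 0.695 |
| 33 | 6 | 0.822 | 0.838 |
| 34 | 7 | 0.720 | 0.741 |
| 35 | 7 | 0.749 | 0.769 |
| 38 | 7 | 0.824 | 0.840 |
| 43 | 8 | 0.826 | 0.843 |
| 44 | 8 | 0.845 | 0.862 |

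From 28 to 43 the probability stays between 0.67 and 0.84. It first passes 0.85 at n = 44, and then only at 24%.

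**The case against.** The strongest reply is that only the inequality is wrong. The section itself equates 18% with 6/34, and the probability of at least 6/34 rounds to 85%, so the author may simply have written greater than where at least was meant. Nothing in the trial depends on the figure: efficacy is secondary, the interim analyses cannot change or stop the study (section 14.4), and the one efficacy test uses 20%. This is fair, and it limits the importance of the point. It does not remove it, because the sentence and the number still disagree and one of them has to change.

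A second reply is that the derivation is unknown. With a uniform prior and 8 of 34 responding, the posterior probability that the true rate exceeds 6/34 is 84.9%. That concerns the true rate, whereas section 14.1 speaks of the observed rate. It is still a reason for the sponsor to confirm the source before choosing a repair.

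Third, objecting to the word ensures could be called a matter of taste, since the sentence is conditional and follows a stated maximum of 34. Not every replacement enlarges the efficacy denominator either: the Full Analysis Set in section 14.2 needs one completed combination cycle, so patients lost before then do not count. Both remarks have some force. The total can still fall to about 28, and then the figure for 34 does not apply.

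Finally, the range of 28 to 43 has no documentary upper end. The patient numbers in section 12.1 would allow 3 × 9 + 24 = 51, and at 24% the probability passes 0.85 at n = 44 (0.862) and n = 49 (0.864). The finding rests on n = 34 and does not need the wider range.

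**Conclusion.** The concern holds. For 34 patients and the section's own rates, the probability that the observed response rate exceeds 18% is 72.0% (true rate 8/34) to 74.1% (24%), not 85%. The printed figure fits the event of at least 6/34, at 84.5–85.9%; that this is its source is an inference, as no derivation is given. The calculation assumes independent responses with one common rate and all 34 patients in the denominator.

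The error should be corrected, but its reach is small. It does not touch dose escalation, determination of the maximum tolerated dose (MTD), or safety. Its cost is a misleading assurance, made worse because the criterion that does give 85% would be met 57–59% of the time by a regimen at the comparator rate.

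**What to change.** Confirm how the 85% was obtained, then amend the sentence in section 14.1 in one of two ways, labelled as applying to n = 34 and with ensures replaced by gives:

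- **A.** Keep the event as exceeding 18% and state 72–74%, adding that the figure is 41% if the true rate is 18%.
- **B.** Reword the event to at least 6/34 (17.6%) and keep about 85%, adding that the figure is 57–59% if the true rate is 6/34 to 18%.

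A makes the stated figure less favourable; B keeps it but shows how weak the criterion is. Neither needs extra patients or a design change. Section 17.7 allows for an amendment or administrative change.

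One optional clarification, not an error: section 14.3.10 tests against 20% without linking this to the 18% and 24% in section 14.1, and the test sentence does not say which patients enter. That section assesses response in the Full Analysis Set, which the synopsis defines across all NOX66 doses. But section 14.3.1 says "All data will be summarized by idronoxil dose group", and the synopsis says response rates "will be summarized for the MTD of the combination by counts and percentages and exact 95% confidence intervals". Name the test population there or in the separate statistical analysis plan (section 14.3.12), and read the test alongside that interval. The protocol claims no power for the test. For information, power at the planning rate is about 4–5% if all 34 are pooled and 0.025 is strict (13 responders needed, level 0.011), or 8–9% with a cut-off of 12 (level 0.027). It is about 2–6% for MTD patients only, taking 16 to 22 (16 expansion patients plus up to 6 from escalation).

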14.2 ANALYSIS SETS

There will be two analysis sets

- Safety Set: All patients treated with at least one dose of idronoxil will be included in the Safety Set (SS). All analyses of safety, toxicity, and PK will be performed for this set.
- Full Analysis Set: All patients who complete at least one cycle of idronoxil + doxorubicin combination therapy will be included in the Full Analysis Set (FAS). Analyses of efficacy, tolerability, and biomarkers will be performed for this set.

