----------------------	--

level. The previous dose level will then be considered for expansion to 6 patients in order to confirm that it is the MTD level. The MTD is defined as the dose level at which no more than 1 patient out of 6 experienced a DLT up to the end of Cycle 1. If in the first group at 800 mg daily (Cohort 1), 2 or 3 patients develop DLTs, then that dose level is considered to be the DLT level and 3 additional patients need not be tested at that level, but lower doses should be studied.

If no DLT is observed at 1800 mg (Cohort 3), dose escalation will be stopped. The proposed highest dose level (1800 mg) will be declared the MTD, and additional patients will be enrolled, if necessary, to ensure that a total of 6 patients are evaluated at this dose level.

The dose escalation scheme is presented in the following table.

Proposed Starting Dose and Dose Escalation Scheme for NOX66

Cohort	1	2	3
Increment	NA	50%	50%
Total daily dose (mg)	800	1200	1800
Daily regimen (mg)	400 BID	600 BID	600 TID

BID = twice daily, TID = three times daily. For each cohort, safety/tolerability and PK data will be collected on Days 1-2 and 7-8 for respective doses.

Assessment of toxicities and decisions about dose escalation and cohort expansion will be made by a Safety Review Committee, that will include at least one Sponsor representative participating investigators, and may also include a cardiologist or other outside consultants at the Sponsor's discretion.

Assessment of DLTs

Patients who withdraw in Cycle 1 for reasons other than safety or toxicity will be replaced. During the 7-day Monotherapy Period, any patient who develops a significant toxicity, as noted below, will be replaced.

For determination of DLT during Cycle 1, toxicity will be graded using the National Cancer Institute-Common Terminology Criteria for Adverse Events (NCI-CTCAE) Version 5.0. Any of the following, if judged to be associated with NOX66 alone or in combination with doxorubicin (i.e., possibly-, probably-, or definitely related to), will be considered a DLT:

- 1) Grade 3 non-hematological toxicities (excluding alopecia) with the following exceptions:
 - i. Grade 3 nausea/vomiting or diarrhea <72 hours with adequate antiemetic and other supportive care
 - ii. Grade 3 fatigue <1 week
 - iii. Grade 3 electrolyte abnormality that lasts 24 to 72 hours (Investigator's discretion for timeframe), is not clinically complicated

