8.3.6 PATIENT REPLACEMENT

The following guidelines will be used to determine when a patient can be replaced

- During the Monotherapy period in the Dose Escalation part of the study, if a patient who is not tolerating the assigned dose of NOX66, may be replaced with another patient, following a joint decision between the Investigator and Medical Monitor. A maximum of 3 replacements is allowed in each dose level in the Monotherapy period.
- If any patient withdraws consent during Monotherapy period or during Cycle 1, he/she will be replaced with another patient.
- If any patient who has not taken at least 80% of the prescribed daily doses of NOX66 during Monotherapy period and Cycle 1, will be replaced with another patient.
- During the Dose Expansion Part, patients who have not completed at least 2 complete cycles of treatment, will be replaced with additional patients, until at least 12 patients have completed 2 cycles.

The recommended phase 2 dose (RP2D) may be defined as the highest dose of the combination administered if no DLTs are observed and the dosage form is acceptable to patients.

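### The efficacy set admits only patients who completed a combination cycle, so early failures drop out of ORR, DCR, PFS and OS; this biases ORR upward and probably the other three

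*Combined protocol and SAP*

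**What the plan says.** Section 14.2 sets up two analysis sets. The Safety Set is everyone with at least one dose of idronoxil and serves safety, toxicity and PK. For the other: "All patients who complete at least one cycle of idronoxil + doxorubicin combination therapy will be included in the Full Analysis Set (FAS". The Synopsis agrees: "All patients who completed at least one cycle of combination therapy (at any NOX66 dose". Of the FAS, Section 14.2 adds: "Analyses of efficacy, tolerability, and biomarkers will be performed for this set".

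Section 14.3.10 carries this through. On response: "Treatment response will be assessed by RECIST v1.1 criteria for patients in the FAS at the end of Cycles 2, 4, and 6". On survival: "Overall survival will be defined as the time in months from initial treatment until death or censoring". PFS has the same starting point, and "The PFS curve will be estimated for the FAS by the Kaplan-Meier method"; OS is likewise estimated on the FAS. The same section tests ORR against 20% with a one-sided exact binomial test at about 0.025.

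Replacement is a separate rule. In the Synopsis: "During the 7-day Monotherapy Period, any patient who develops a significant toxicity, as noted below, will be replaced". In Section 8.3.6: "During the Dose Expansion Part, patients who have not completed at least 2 complete cycles of treatment, will be replaced with additional patients", which continues until at least 12 patients have two cycles. The Synopsis and Section 15.2.2.3 also replace Cycle 1 withdrawals that are not for safety reasons.

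The Synopsis and Sections 11.1.2.2 and 11.5.2 divide response counts by *All* without saying all of whom.

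**The concern.** Entry to the efficacy set depends on an outcome that occurs after the PFS and OS clock has started. A patient who fails before completing Cycle 1 contributes no event and no non-response. Three consequences follow.

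- **ORR.** Section 11.4.4 schedules the first on-treatment scan at the end of Cycle 2. An excluded patient could count as a responder only on an Early Termination or unscheduled scan, so exclusion removes non-responders almost exclusively. The test against 20% tilts towards rejection.
- **OS, and less directly PFS and DCR.** Every FAS patient is known to have survived to the end of Cycle 1, yet that time is credited to the curve.
- **Visibility.** Some lost patients may be replaced, so the FAS count can partly hide the loss.

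Efficacy at the MTD is a secondary objective (Section 7.2), so what is at stake is how the first activity signal is read.

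**Working it through.** **The plan's own figure.** Section 14.1 gives an 85% probability that the observed rate exceeds 18%. With n = 34 and p = 8/34, P(X ≥ 6) = 0.845, so the figure reproduces as *at least 6 of 34*. Strictly more than 18% needs 7 responders: P(X ≥ 7) = 0.720. It makes no allowance for early loss and does not bear further on this point.

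**Guaranteed survival.** If completing a cycle means the 21-day cycle, the window is 21 days in expansion. In escalation it is 12 days of lead-in (Synopsis, Study Period) + 21 = 33 days.

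**Inputs for the ORR test.** Null rate 0.20 and level 0.025 come from Section 14.3.10. The Synopsis summarises response at the MTD, so I take n = 22: 6 patients confirming the MTD plus 16 in expansion. The share q lost before completing Cycle 1 is not in the documents; I assume 3%, 5%, 10% and 20%. Excluded patients are taken as non-responders.

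**Formulas.** If the true rate among all patients is 0.20, the FAS rate is r = 0.20/(1 − q).

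- *Critical value c(n)*: the smallest c with P(X ≥ c | n, 0.20) ≤ 0.025. It is 9 for n = 20 to 22 and 8 for n = 17 to 19. At n = 22 the attained level is 0.020.
- *No refill*: the FAS size M is Binomial(22, 1 − q), and error = Σ P(M = m) × P(X ≥ c(m) | m, r).
- *Full refill*: error = P(X ≥ 9 | 22, r).
- *Random loss*: the no-refill sum with r replaced by 0.20, to separate selection from the discreteness of the test.

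| Lost before completing Cycle 1 | 3% | 5% | 10% | 20% |
|---|---|---|---|---|
| FAS rate r when the true rate is 20% | 20.6% | 21.1% | 22.2% | 25.0% |
| Error, no refill | 0.021 | 0.022 | 0.029 | 0.051 |
| Error, full refill | 0.024 | 0.028 | 0.038 | 0.075 |
| Error, random loss, no refill | 0.017 | 0.016 | 0.016 | 0.014 |

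Error passes 0.025 at about 7.4% lost without refill and about 3.4% with full refill.

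**Which case is nearer.** Expansion enrols 16, and replacement is required only until 12 have two cycles, so up to 4 can be lost before it is needed. Counting Cycle 1 losses alone, P(more than 4 of 16 lost) is 0.1%, 1.7% and 20% at q = 5%, 10% and 20%. Cycle 2 losses would add to this. At modest loss, no refill is the nearer case.

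**Single results.** Near the threshold, 8/22 (36.4%) gives p = 0.056, while dropping three early failures gives 8/19 (42.1%), p = 0.023. Near the planned rate nothing changes: 5/22 gives p = 0.457 and 5/19 gives p = 0.327.

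**The case against.** The best defence is that this is Phase I, efficacy is preliminary, Section 14.1 says the sample size has no statistical basis, and no decision rule hangs on the ORR test. Loss before the end of Cycle 1 may also be small: entry requires ECOG 0–2 and a life expectancy of at least 6 months. The nearest figures in Section 6.1 are 3% (doxorubicin alone) and 18% (with ifosfamide) unable to complete six cycles because of adverse events. They leave out progression and death but span six cycles, so they do not supply a Cycle 1 rate. At 3% lost, neither error above reaches 0.025. This limits the size of the point but does not remove the selection. Section 14.3.12 defers detail to a further SAP, which could add an all-treated analysis; the present text states none.

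Some stronger readings are tempting and are not supported.

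- *The loss is invisible.* The Synopsis says replacement takes enrolment above 34, the Safety Set holds every treated patient, and Section 14.3.2 summarises disposition. Only the FAS count could mask the loss, and only partly: a patient with a Cycle 1 DLT stays evaluable (Section 8.3.5) and is not clearly replaced, and monotherapy replacements are capped at three per dose level.
- *Median PFS is inflated by the full 21 or 33 days.* NOX66 dosing ends on Day 7, so a patient can progress later in the cycle and still complete it. The window guarantees survival, not freedom from progression.
- *The distortion applies to a pooled 34.* Section 14.1 uses 34, but the Synopsis summarises response at the MTD and Section 14.3.1 summarises by dose group.
- *The primary tolerability objective is compromised.* Adverse events are analysed on the Safety Set, with a separate summary of onset before doxorubicin (Section 14.3.4). Of the tolerability measures, only the Suppository Acceptance Questionnaire is left on the FAS (Section 14.3.11).

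**Conclusion.** The concern stands for the secondary efficacy analyses. The efficacy set is chosen by a post-treatment outcome, PFS and OS are timed from before that outcome, and nothing in the plan shows what the restriction does. The upward direction is near certain for ORR and probable for DCR, PFS and OS; I put no size on the last three. With 22 patients at the MTD and 3% to 20% lost early, the test's error runs from 0.021 to 0.051 without refill and from 0.024 to 0.075 with full refill, against 0.020 with no loss. These figures rest on assumed loss rates, on excluded patients being non-responders, and on 22 being the tested set. The bias vanishes if everyone completes Cycle 1, and only results close to the threshold would change sides. It should be corrected before efficacy is analysed.

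**What to change.** In the Synopsis and Sections 14.2 and 14.3.10:

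- Make the main efficacy set all patients who received at least one dose in Cycle 1 of the combination, including any later replaced, with PFS and OS timed from Cycle 1 Day 1. This suits the objective better than the Safety Set, which would count escalation patients who stopped in monotherapy as failures of a combination they never received.
- Count patients without an evaluable post-baseline scan as non-responders and as not disease-controlled.
- State that *All* in the Synopsis and Sections 11.1.2.2 and 11.5.2 means this set.
- Report two supportive sets: (a) the Safety Set, timed from first dose; (b) one-cycle completers, defined as completing the 21-day cycle. Section 8.1.1 already describes a cycle that way, but Section 14.2 does not say so.
- Summarise the Suppository Acceptance Questionnaire on the Safety Set (Section 14.3.11).

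Most of the data are already planned: Section 11.2.2 keeps patients in tumour follow-up after they stop treatment, and note 15 to Table 4 brings early leavers in for assessment within 28 days. The cost is wording, two supportive tables and slightly less favourable efficacy figures.
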